Sacroiliitis (inflammation of the sacroiliac joints) is the radiological hallmark of axSpA, but other spinal lesions include spondylitis (inflammation of the vertebral bodies) spondylodiscitis (inflammation of the vertebral discs), enthesitis (inflammation of the spinal ligament insertion points) and the formation of syndesmophytes in chronic disease. Historically, axSpA has been diagnosed using plain radiographs of the sacroiliac joints to assess for sacroiliitis according to the 1984 modified New York criteria for AS [15]. However, over the last 20 to 30 years, cross-sectional imaging with computed tomography (CT) and magnetic resonance imaging (MRI) has become increasingly utilised. CT scans can better detect chronic bony changes in axSpA, including erosions, sclerosis and ankylosis, compared with radiographs [16-19]. However unlike MRI, they are unable to identify acute inflammatory changes related to bone marrow oedema or chronic changes related to fatty atrophy and MRI is much more effective at detecting early signs of axSpA [16, 20-22]. CT scans also pose higher ionising radiation exposure. MRI does not pose an ionising radiation risk and has therefore been recommended for the assessment of SpA in the 2009 ASAS guidelines [16]. Regarding PsA, this can be diagnosed using the CASPAR criteria [23].

The acute inflammatory changes of axSpA are best seen on MRI using dedicated fluid sensitive sequences such as a fat saturated T2-weighted sequence or a short tau inversion recovery (STIR) sequence. The typical active inflammatory lesions of the sacroiliac joint on MRI include bone marrow oedema, capsulitis, enthesitis and synovitis, and the chronic lesions include sclerosis, erosions and ankylosis [24]. The typical axSpA MRI spinal lesions include spondylitis, spondylodiscitis, enthesitis and syndesmophytes [16].

MRE imaging has been shown to be a useful tool in the diagnosis and assessment of potential complications for patients with CD [25, 26]. The majority of CD patients will have been reviewed by secondary care specialists in gastroenterology, and most will have had cross-sectional imaging in the form of MRE imaging to assess the extent of their CD. These scans also capture the axial (spine and

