3.2 Objectives

We hypothesise that existing cross-sectional imaging (MRE) from the routine NHS care of patients with CD can be used to screen patients for evidence of axSpA, thereby prompting onward referral to the rheumatology department for further management.

The objectives of this study are therefore to determine:

1. the validity, sensitivity, specificity and area under the ROC curve of MRE as a screening tool for axSpA in CD, using dedicated axial MRI scans with clinical assessment as the gold standard.
2. the proportion of patients with evidence of axSpA on MRE imaging who fulfill the 2009 ASAS criteria for axSpA, modified New York criteria for AS and the CASPAR criteria for PsA.
3. the proportion of these patients proceeding to non-pharmacological and pharmacological treatment of their axSpA, as a surrogate measure of change in clinical care as a result of MRE screening.
4. the extra-articular features associated with axSpA in CD, in order to better characterise the clinical phenotype of eSpA.
5. whether the site of CD (colon, ileum, etc.) predicts the occurrence of axSpA.

4. Study design

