4.3 ProSpA-CD-Assess phase

4.3.1 Assessment of patients with lesions on MRE consistent with axSpA (cases)

Patients with lesions on MRE consistent with axSpA (and no known diagnosis of SpA) will be informed by telephone and letter by the gastroenterology team and referred to [name] NHS rheumatology SpA clinic. They will also be sent separately an invitation letter, participant information sheet (PIS) and reply slip (study interest form with a stamped-addressed envelope for returns) for the ProSpA-CD-Assess phase of the study by the gastroenterology team. CD subjects with a known diagnosis of SpA who are already under review by rheumatology and who have lesions on MRE consistent with axSpA will also be considered as cases and will be sent an invitation letter, PIS and study interest form. However, they will instead be invited to attend the rheumatology SpA research clinic to be assessed for axSpA (with the control group) as this will be considered to be outside of their routine NHS care.

In the NHS SpA clinic, the patients will be assessed by a single rheumatologist ([name], in a supernumerary capacity with salary funded by the research grant) for clinical evidence of axSpA *as per* standard of care using the 2009 ASAS criteria for axSpA, modified New York criteria for AS and CASPAR criteria for PsA (see Appendices 5, 6 & 7). The assessment will include a clinical history, examination (including BASMI, 68 tender joint count, 66 swollen joint count, the SPARCC enthesitis index and for skin or nail psoriasis), PROMs (BASDAI, BASFI, VASbp, ASDAS and HAQ-DI), blood samples (FBC, renal function, LFTs, CRP and ESR unless performed in the preceding month, and HLA-B27 unless previously performed) and stool samples (the monitoring of IBD luminal activity with faecal calprotectin is well established [41, 42]; stool samples will therefore also be collected to measure faecal calprotectin concentrations unless performed in the preceding month). During the consultation, the ProSpA-CD-Assess phase of the study will also be discussed further and patients will be provided with the opportunity to ask any questions they may have regarding the study. If they agree to participate in the study and meet the inclusion criteria, then written informed consent will be taken. The blood and stool tests will be performed as per standard of care if clinically indicated or for research and funded by the research grant if not clinically indicated.

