4.3.2 Assessment of subjects with no lesions on MRE consistent with axSpA (controls)

Subjects (including those with a known diagnosis of SpA) who have consented to having their MRE scans reviewed, but who do not have lesions consistent with axSpA, will be informed in writing of this by the gastroenterology team. They will also be advised that they may be invited to enter the study as a control subject if they are randomly selected through matching (age and sex) to the enrolled 'MRE+ cases' (1:1 ratio). Matched potential control subjects will then be sent an invitation letter, PIS and reply slip (study interest form with a stamped-addressed envelope for returns) by the gastroenterology team to attend the rheumatology SpA research clinic to be assessed by [name] for clinical evidence of axSpA. CD subjects with a known diagnosis of SpA who are already under review by rheumatology and who have lesions on MRE consistent with axSpA will also be invited to attend this clinic for review outside of their routine NHS care but will be considered as cases. Informed consent for study participation in the SpA research clinic will be performed at the start of the consultation. The same clinical assessments, blood and stool samples and dedicated axial MRI scan of the spine and sacroiliac joints will be performed in this control group and in the group of CD subjects with a known diagnosis of SpA who are MRE+ as in the other cases, but will be funded by the research grant unless clinically indicated.

Control subjects in whom there is no evidence of axSpA (by ASAS, modified New York or CASPAR classification criteria) will be informed by letter, which will also be copied to the subjects GP and gastroenterology consultant. Control subjects who do have evidence of axSpA will be informed by letter (also copied to GP and gastroenterology consultant) and asked to return to [name] NHS rheumatology SpA clinic for ongoing care. CD subjects who already have a diagnosis of SpA (both in the control group and cases group) and are already under review by a rheumatology team will be informed by letter of the research clinic outcome and will be followed up as planned by their primary rheumatology team. We will also send a copy of the clinic letter to their GP, gastroenterology consultant and named rheumatology consultant to inform them of the clinic findings and to notify them of any outstanding tests/ management plans that may need to be considered at the next clinic review.

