6.4 Blood sampling (total of 40ml)

20ml for standard of care : FBC, LFTs, renal function, CRP and ESR (if not performed within the last one month). *HLA-B27* if not previously performed.

20ml if subjects consent to the research element of the study : for storage and later analysis (serum biomarkers, proteomics and genotyping).

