Appendix 6: Modified New York Criteria for the diagnosis of ankylosing spondylitis [15].

Requires radiological criterion & ≥ 1 clinical criterion

Radiological criterion

Sacroiliitis grade ≥ 2 bilaterally or grade ≥ 3 unilaterally

Clinical criterion

1. Inflammatory low back pain & stiffness $\geq 30m$ that improves with exercise and is not relieved by rest
2. Reduced motion of the lumbar-spine in both sagittal & frontal planes
3. Limited chest expansion

(having excluded spinal fracture, intervertebral disc disease & fibromyalgia.)

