Appendix 7: Classification Criteria for Psoriatic Arthritis (CASPAR) [23].

To meet the CASPAR (CIAssification criteria for Psoriatic ARthritis) criteria, a patient must have inflammatory articular disease (joint, spine, or enthesal) plus ≥ 3 points from the following 5 categories:

1. Evidence of current psoriasis, a personal history of psoriasis, or a family history of psoriasis.

Current psoriasis is defined as psoriatic skin or scalp disease present today as judged by a rheumatologist or dermatologist.

† A personal history of psoriasis is defined as a history of psoriasis that may be obtained from a patient, family physician, dermatologist, rheumatologist, or other qualified health care provider.

A family history of psoriasis is defined as a history of psoriasis in a first- or second-degree relative according to patient report.

2. Typical psoriatic nail dystrophy including onycholysis, pitting, and hyperkeratosis observed on current physical examination.

3. A negative test result for the presence of rheumatoid factor by any method except latex but preferably by enzyme-linked immunosorbent assay or nephelometry, according to the local laboratory reference range.

4. Either current dactylitis, defined as swelling of an entire digit, or a history of dactylitis recorded by a rheumatologist.

5. Radiographic evidence of juxtaarticular new bone formation, appearing as ill-defined ossification near joint margins (but excluding osteophyte formation) on plain radiographs of the hand or foot.

(The CASPAR criteria have specificity of 98.7% and sensitivity of 91.4%)

(† Current psoriasis is assigned a score of 2; all other features are assigned a score of 1.)

Appendix 8: The spondyloarthritis research consortium of Canada (SPARCC): Magnetic Resonance Imaging index for scoring inflammation in the spine[43].

SCORING METHODOLOGY

1. All scores are dichotomous – present or absent.
2. After scanning the entire spine, 6 discovertebral levels are selected for scoring. These levels are chosen as representing the 6 most abnormal levels on the STIR sequence. Levels scored at a second time point are the same as those on the first.
3. After selecting levels, three consecutive sagittal slices are chosen for scoring at each level representing the most abnormal slices for that level.
4. Only abnormalities on the STIR sequence are scored. T1 SE images are included for anatomical reference.

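### Objective 2 promises modified New York and CASPAR proportions, but no visible procedure list schedules a plain radiograph or rheumatoid factor, and no rule covers missing criterion items

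*Combined protocol and SAP*

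**What the plan says.** - **Outcome.** Objective 2 asks what proportion of MRE-positive patients fulfil the ASAS criteria, "modified New York criteria for AS and the CASPAR criteria for PsA" (section 3.2, repeated in 1.3). Section 8.2 plans a percentage of cases meeting criteria for axSpA.
- **Who applies the criteria.** One rheumatologist assesses cases in clinic "using the 2009 ASAS criteria for axSpA, modified New York criteria for AS and CASPAR criteria for PsA" (section 4.3.1). For controls, section 4.3.2 judges evidence of axSpA "by ASAS, modified New York or CASPAR classification criteria".
- **Modified New York.** Appendix 6: "Requires radiological criterion & ≥ 1 clinical criterion". The radiological part is a sacroiliitis grade of at least 2 on both sides or at least 3 on one. Section 2.1 describes the historical use of "plain radiographs of the sacroiliac joints to assess for sacroiliitis according to the 1984 modified New York criteria for AS".
- **CASPAR.** Appendix 7 requires inflammatory articular disease plus at least 3 points. Current psoriasis counts 2 and every other feature 1. Item 3 is "A negative test result for the presence of rheumatoid factor by any method except latex". Item 5 is "Radiographic evidence of juxtaarticular new bone formation" on films of the hand or foot.
- **What is collected.** Section 6.4 lists "FBC, LFTs, renal function, CRP and ESR (if not performed within the last one month"), with HLA-B27 if never done. Sections 1.6, 4.1, 4.3.1 and 7.1 give the same blood tests. The only study imaging is the existing MRE and a dedicated non-contrast MRI (4.3.3, 6.6, Appendix 2).
- **Missing data.** Section 8.3 deals only with help in completing questionnaires.

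**The concern.** Two of the three proportions promised by objective 2 depend on items that the plan does not schedule. If it is followed as written, a reader of the results could not tell whether a modified New York percentage came from old radiographs, from MRI graded in some unstated way, or from counting every case without a film as not fulfilling. For CASPAR, two of the five categories would be blank unless found in earlier records, and the plan does not say how a blank is scored. The reported figure would then depend on an unwritten choice, and two analysts with the same data could report different proportions.

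**Working it through.** The plan states no figure on this point that needs reproducing. The check compares what each criterion needs with what the plan schedules, then counts CASPAR points.

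**1. Denominator.** Section 8.1 expects about 445 scans to review and takes 15% as the lower of two published prevalences: 445 × 0.15 = 66.75, hence its figure of at least 66 cases. Objective 2 concerns these cases only.

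**2. Required against scheduled.**

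| Item | Required by | Scheduled? |
|---|---|---|
| Graded radiological sacroiliitis | Appendix 6, compulsory | No radiograph listed |
| Skin psoriasis (2 if current; 1 if personal or family history) | CASPAR item 1 | Yes: history and examination (4.3.1, 6.3) |
| Nail disease (1) | CASPAR item 2 | Yes (4.3.1, 6.3) |
| Negative rheumatoid factor (1) | CASPAR item 3 | No |
| Dactylitis (1) | CASPAR item 4 | Not listed; history or examination might capture it |
| Hand or foot radiograph (1) | CASPAR item 5 | No |

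**3. Modified New York.** MRE and MRI are scored 0–2 for joint contour and 0–3 for marrow signal (4.2.1, 4.3.3). The MRI also receives the SPARCC index, which counts STIR abnormalities only (Appendices 8 and 9). No section converts any of these into the grades used in Appendix 6. The compulsory criterion therefore has no input from scheduled data.

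**4. CASPAR maximum.**
- All items: 2 + 1 + 1 + 1 + 1 = 6.
- Without rheumatoid factor and radiograph: 6 − 1 − 1 = 4.
- If dactylitis is also not recorded: 4 − 1 = 3.

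**5. One patient.** Current psoriasis (2) plus a truly negative rheumatoid factor (1) gives 3, which meets the threshold. With the assay not done and scored 0, the total is 2, which does not.

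**6. All item patterns** (patterns, not patients; articular disease assumed present).
- Psoriasis has three levels and the other four items two each: 3 × 2 × 2 × 2 × 2 = 48 patterns, of which 31 reach 3 points.
- On psoriasis, nail and dactylitis alone there are 3 × 2 × 2 = 12 patterns. Four already reach 3. One (no points) cannot, since 0 + 2 = 2. Seven are undetermined.
- Each of those four allows 2 × 2 = 4 combinations of the missing items, so 4 × 4 = 16 of the 31 qualifying patterns are recognised and 31 − 16 = 15 are lost when blanks score 0.
- With only one of the two 1-point items missing, 24 of 31 are recognised. Adding rheumatoid factor thus recovers 24 − 16 = 8 of the 15.

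**7. Opposite rule.** If an untested rheumatoid factor is taken as negative, a patient who is in fact positive, has no radiographic point and has exactly 2 clinical points is wrongly counted as fulfilling. Four patterns do this: current psoriasis alone, and any two of psoriasis history, nail disease and dactylitis. The direction of error depends on the rule.

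**8. Patients.** The documents give no frequency of psoriasis in Crohn's disease. Purely as an assumption, if 2% to 10% of 66 cases had current psoriasis without nail disease or dactylitis, then 66 × 0.02 = 1.3 to 66 × 0.10 = 6.6, or about 1 to 7 cases, would be undetermined through that pattern alone.

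**The case against.** The strongest reply is that the information may exist without being scheduled. Appendix 6 does not itself name a modality, and section 2.1 links radiographs to modified New York in a historical account. Section 4.3.1 has the criteria applied under standard care with a clinical history, and section 7.1.3 provides consent to consult medical records. Earlier radiographs or rheumatoid factor results could be found for some cases. This stands as a limit: the gap concerns scheduled data. It does not close the gap, because the plan does not commit to retrieving, reading or grading such material, and availability may be selective. The documents do not show which patients would have it.

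The Appendix 1 flow chart and the content of Appendix 5 were not visible, so they could not be checked. The text lists and Appendix 2 agree with one another.

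Three stronger readings are tempting, and the documents do not support them:

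- **That none of 132 or more subjects can be scored.** Objective 2 covers the cases, at least 66; the matched controls fall outside it. Records may also serve some cases.
- **That CASPAR is necessarily biased downward.** This follows only if blanks score 0, and the plan states no such rule.
- **That the gold standard is compromised.** The reference is dedicated MRI with clinical assessment (section 3.1), and the plan does not say how the three criteria sets enter it. Section 4.3.2 joins them with an or, so a missing result matters only where no other set is met. HLA-B27 and MRI are collected.

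**Conclusion.** The point holds for objective 2. On the visible lists, scheduled data supply no input for the compulsory modified New York criterion and at most 4 of 6 CASPAR points, or 3 if dactylitis goes unrecorded. With blanks scored 0, 16 of 31 qualifying CASPAR patterns are recognised; with rheumatoid factor assumed negative, error in the other direction becomes possible. The number of patients affected cannot be derived from the documents.

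This is more than missing detail, because the plan as written cannot properly deliver two of its three stated proportions. It is also bounded: objective 2 is descriptive, the ASAS proportion is not challenged here, and no effect on the sensitivity and specificity aim is shown. The conclusion assumes that the unseen Appendix 1 adds no radiograph or rheumatoid factor.

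**What to change.** 1. **Rheumatoid factor.** Add it to the Assess-visit bloods where no result is on record. Where routine bloods are skipped because they were done in the preceding month, use a separate draw, or stored research serum if consent covers it.
2. **Dactylitis.** Add current dactylitis, and any history recorded by a rheumatologist, to the examination items in sections 4.3.1 and 6.3.
3. **Modified New York.** Report it only for cases with an existing gradable pelvic radiograph, name who grades the films, and show that denominator beside the total number of cases. Report any MRI-based grading separately, not as modified New York.
4. **CASPAR.** Record the radiographic item as not assessed when absent, and report fulfilment as a lower bound. Once the other four items are complete, only cases with exactly 2 points could change, so give their number.
5. **Missing items.** State these rules in sections 8.2 and 8.3 before scoring begins.

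The cost is one added assay for cases without a result (the documents give no price), an occasional extra draw, one examination item and some wording. No new imaging is needed. The downside is a smaller, selected denominator for modified New York, which the report should acknowledge.
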